1.0 Objectives

- 1.1 Purpose: Evaluate whether the Social Support Aid (SSA) exerts positive benefits for people with memory concerns' (PWMCs') social connections, communication, and quality of life via an embedded experimental mixed methods design that combines the collection and analysis of qualitative data within a traditional randomized controlled trial (RCT) design.

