3.0 Study Endpoints/Events/Outcomes

- 3.1 Primary Endpoint/Event/Outcome:

Change in Dementia Quality of Life [Time Frame: Baseline, 3-months, and 6-months]

The 21-item modified Dementia Quality of Life instrument is a self-report survey that assesses various domains of quality of life in the person with dementia.

Change in Cantril quality of life ladder [Time Frame: Baseline, 3-months, and 6-months]

The Cantril quality of life ladder is a single item survey that asks respondents to rate their overall quality of life on a scale of 0 (bottom of the latter) to 10 (top of the ladder).

- 3.2 Secondary Endpoint(s)/Event(s)/Outcome(s):

Pleasant events and activities of person with memory concerns [Time Frame: 3-months and 6-months]

The Pleasant Events and Activities-AD Schedule Short Form is a 17-item self-report survey that measures the degree of enjoyment persons with dementia have engaging in a range of activities.

Change in the frequency and quality of social interactions of persons with memory concerns [Time Frame: Baseline, 3-months, and 6-months]

Series of weekly, self-report calendar measures on types and quality of social interactions, developed for this study.

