5.0 Procedures Involved

5.1 Study Design:

A parallel randomized controlled pilot trial design.

5.2 Study Procedures:

“Following completion of the baseline survey, participants were randomly assigned to either receive the technology or to continue with usual care. Participants were randomized at a ratio of 1:1 using a random number generator. Neither the participants nor researchers were blinded to randomization group. Research assistants met with participants in the intervention group in-person to provide the mobile phone and smartwatch and demonstrate how to use the SSA technology. Participants were given the technology to use at their discretion, and there was no requirement for how many times they had to use the SSA. Throughout the study, research assistants and the SSA developer provided technical support and answered questions regarding the technology. Participants in the control group were given the technology free of charge after completing the study.” (see <https://www.ncbi.nlm.nih.gov/pmc/articles/PMC6715400/>)

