17.0 Statistical Considerations

17.1 Data Analysis Plan From:

<https://www.ncbi.nlm.nih.gov/pmc/articles/PMC6715400/>.

“Recruitment, Randomization, and Retention

Chi-square and t tests were used to determine if participant demographics in the intervention and control groups were significantly different ($P<.05$). Chi-square and t tests were also used to compare participants who were lost to follow-up with those who were not.

Feasibility and Utility

Participants in the intervention group were asked to complete an additional survey at 3 and 6 months to assess their perceptions of feasibility and utility. This checklist included 15 Likert scale items asking participants to rate their level of agreement with statements such as “the technology works well,” “SSA was easy to use,” and “my relative felt lost using SSA” ($\alpha=.89$).

Assessment of Intervention Effect

Descriptive statistics were calculated for measures of quality of social interaction and quality of life. Social interaction quality was measured by asking participants to rate their satisfaction with the following types of communication: visits, phone calls, mail correspondence, and computer correspondence. Quality of life was measured using the Pleasant Events Schedule-Alzheimer’s Disease (PES-AD; frequency $\alpha=.84$; enjoyment $\alpha=.76$) and Dementia Quality of Life (DQoL; $\alpha=.92$). The PES-AD asks with what frequency and level of enjoyment the person with memory loss experiences a list of pleasant activities (eg, being outside, listening to music, laughing). The DQoL asks participants to use a Likert scale to rate how often the person with memory loss feels a certain way (eg, satisfied, cheerful, angry, worried).

We imputed missing data using a Markov chain Monte Carlo method to conduct a five-fold multiple imputation. Analyses were conducted as intention to treat. Change scores were calculated to determine differences between outcomes at baseline and 6 months. To determine whether changes in satisfaction and quality of life in the intervention group were significantly different than changes in the control group, t tests were used. Statistical significance was assessed using two-tailed tests with a significance level of $P=.05$.

SOCIAL PROTOCOL (HRP-580)

PROTOCOL TITLE: Social Support Aid for People with Dementia

VERSION DATE: 5/8/2017

Qualitative Analysis

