17.2 Power Analysis: n/a

17.3 Statistical Analysis: Please see section 17.1 above

17.4 Data Integrity: Data cleaning and review of frequencies and other univariate

procedures are used to ensure that the final analytic data sets are accurate.

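### Section 17.1 answers an efficacy objective with P=.05 t tests and no confidence interval in a 48-person pilot, so a non-significant result cannot be read as no benefit

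*Combined protocol and SAP*

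**What the plan says.** Section 1.1 sets one objective: to "Evaluate whether the Social Support Aid (SSA) exerts positive benefits for people with memory concerns' (PWMCs') social connections, communication, and quality of life". It describes a mixed-methods study that "combines the collection and analysis of qualitative data within a traditional randomized controlled trial (RCT) design". Section 3.1 lists two primary outcomes, "Change in Dementia Quality of Life [Time Frame: Baseline, 3-months, and 6-months" and "Change in Cantril quality of life ladder [Time Frame: Baseline, 3-months, and 6-months", each over those three time points. Section 3.2 adds pleasant events and social interactions.

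Section 5.1 labels the study "A parallel randomized controlled pilot trial design". Section 11.1 gives 48 participants without a derivation, and the power entry reads "17.2 Power Analysis: n/a".

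Section 17.1 (Assessment of Intervention Effect) provides descriptive statistics, five-fold multiple imputation, an intention-to-treat analysis, and t tests comparing baseline-to-6-month change between arms. The decision rule is: "Statistical significance was assessed using two-tailed tests with a significance level of $P=.05". No confidence interval for the arm difference is described.

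The same section opens with recruitment, randomization and retention, then turns to how workable the technology was: "Participants in the intervention group were asked to complete an additional survey at 3 and 6 months to assess their perceptions of feasibility and utility". It closes with a thematic analysis of interviews with 13 intervention-arm participants about how and why the SSA did or did not work.

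**The concern.** The objective asks whether the SSA brings benefit. For the quantitative outcomes, the only inferential tool described is a test that returns significant or not significant. No effect size, SD or power figure says what that test could detect. A reader who meets a non-significant P value, with no interval beside it, may take it as the answer to section 1.1.

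At stake is the interpretation. If the data are compatible both with no effect and with a benefit of half a standard deviation, the report should show that range. A P value alone hides it.

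**Working it through.** **The plan's own figures.** There is no power or precision figure to reproduce. The one related figure that can be checked is retention in section 13: 44/48 = 91.7%, which agrees with the stated 92%.

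**Inputs**
- 48 randomized (sections 11.1 and 13), allocated 1:1 (section 5.2). Arm sizes are not stated, so I assume 24 per arm.
- All four losses were in the intervention arm (section 13), so completers are 24 − 4 = 20 against 24 on that assumption.
- Two-sided 5% t test on change scores (section 17.1).
- No SD or meaningful difference is given. Effects are in units of the SD of the change score, and the true effects d below are illustrative.

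**Width of the 95% interval.** Half-width = t(0.975, n1+n2−2) × √(1/n1 + 1/n2).
- 24 v 24: 2.013 × √(1/24 + 1/24) = 2.013 × 0.2887 = 0.581 SD.
- 20 v 24: 2.018 × √(1/20 + 1/24) = 2.018 × 0.3028 = 0.611 SD.
- Sensitivity to the assumed split, 20 v 28 randomized: 2.013 × √(1/20 + 1/28) = 2.013 × 0.2928 = 0.589 SD. Moderate imbalance hardly matters.

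The half-width is also the smallest observed difference that reaches P<.05. An observed difference of 0.3 SD would have an interval of 0.30 ± 0.58, that is −0.28 to 0.88 SD, and would be called non-significant.

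**Chance of a significant result.** Noncentral t with noncentrality d / √(1/n1 + 1/n2). For 24 v 24 this is 0.3/0.2887 = 1.04 at d = 0.3 and 0.5/0.2887 = 1.73 at d = 0.5.

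| True benefit (SD) | 24 v 24 | 20 v 24 |
|---|---|---|
| 0.2 | 10% | 10% |
| 0.3 | 17% | 16% |
| 0.5 | 40% | 37% |
| 0.8 | 77% | 73% |

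So with 24 per arm, a true benefit of 0.3 SD is missed about 83% of the time (100 − 17) and one of 0.5 SD about 60% of the time (100 − 40). Power reaches 80% only at about 0.83 SD (24 v 24) or 0.87 SD (20 v 24).

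The plan analyses by intention to treat with multiple imputation, so the 20 v 24 row is only a guide to the effect of the missing data. The interval to report is the pooled one.

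**The case against.** **Pilots need no power calculation.** This stands. The missing calculation is not the fault, and more participants are not being asked for. The point is only how the test results are presented and read.

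**The t test is not the whole answer.** This stands in part. Section 17.1 also gives descriptive statistics, and the interviews address whether and why the SSA worked. A reader might infer that the protocol will treat non-significance as proof of no benefit. No section says so. What remains is that nothing in the plan guards against that reading, and the one quantitative inference described does not show the uncertainty.

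**Feasibility has been overlooked.** A reader might infer this because sections 1 and 3 contain no feasibility item, and might go on to conclude that feasibility should replace the quality-of-life outcomes as primary. The documents do not support either step. The checklist is scheduled in section 5.3, recruitment, retention and feasibility are analysed in section 17.1, and retention is reported in section 13. Section 26.1 says the study is complete. Changing the primary outcomes now, towards measures whose results are already on file, would be retrospective outcome switching. Nor do the documents mention a later full trial or progression criteria that these measures were meant to serve.

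**Intervals may have been reported anyway.** Section 17.1 is an excerpt from a publication, and its silence does not show that the publication gave none. This also stands, and it limits the point to what the plan describes.

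**Conclusion.** The point holds as one of analysis and interpretation. With about 24 per arm, the 95% interval for an arm difference spans roughly ±0.6 SD, and true benefits of 0.3 to 0.5 SD would be non-significant about 83% to 60% of the time. A non-significant t test in this trial cannot be taken as evidence that the SSA has no benefit, and section 17.1 as written describes nothing that would show this to the reader.

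These sizes rest on an assumed equal split, on effects expressed in SD units because no SD is given, and on illustrative true effects. Reasonable changes to the arm sizes do not alter the conclusion. The point does not extend to the choice of primary outcomes, to the absence of a power calculation as such, or to a claim that feasibility was left out of the plan. It is an inexpensive improvement to how results are reported.

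**What to change.** In section 17.1:
- For each quality-of-life and social-interaction outcome, report the arm difference in change with its 95% confidence interval, pooled over the five imputations (Rubin's rules). Include the Cantril ladder, which section 3.1 lists as primary but section 17.1 does not name.
- State that these are pilot estimates and that a non-significant P value will not be taken as absence of benefit.

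Keep DQoL and the Cantril ladder as the listed primary outcomes. Recruitment, retention by arm and the 15-item checklist, all obtainable from data already collected, may be named as feasibility outcomes only if explicitly labelled post hoc.

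**Cost.** A few sentences, and intervals from data and imputations already in hand. No new participants or measurements are needed. The trial gives up a yes/no efficacy verdict, for which it states no power basis.

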2.0 Background

- 2.1 Significance of Research Question/Purpose: See <https://aging.jmir.org/2019/1/e13378/>
- 2.2 Preliminary Data: See <https://aging.jmir.org/2019/1/e13378/>
- 2.3 Existing Literature: See <https://aging.jmir.org/2019/1/e13378/>

3.0 Study Endpoints/Events/Outcomes

- 3.1 Primary Endpoint/Event/Outcome:

Change in Dementia Quality of Life [Time Frame: Baseline, 3-months, and 6-months]

The 21-item modified Dementia Quality of Life instrument is a self-report survey that assesses various domains of quality of life in the person with dementia.

Change in Cantril quality of life ladder [Time Frame: Baseline, 3-months, and 6-months]

The Cantril quality of life ladder is a single item survey that asks respondents to rate their overall quality of life on a scale of 0 (bottom of the latter) to 10 (top of the ladder).

- 3.2 Secondary Endpoint(s)/Event(s)/Outcome(s):

Pleasant events and activities of person with memory concerns [Time Frame: 3-months and 6-months]

The Pleasant Events and Activities-AD Schedule Short Form is a 17-item self-report survey that measures the degree of enjoyment persons with dementia have engaging in a range of activities.

Change in the frequency and quality of social interactions of persons with memory concerns [Time Frame: Baseline, 3-months, and 6-months]

Series of weekly, self-report calendar measures on types and quality of social interactions, developed for this study.

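### The PES-AD secondary outcome defined in section 3.2 (enjoyment, at 3 and 6 months, no baseline) is not the one analysed in section 17.1 (frequency and enjoyment, change from baseline to 6 months), and which score is the secondary result is left open

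*Combined protocol and SAP*

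**What the plan says.** Section 3.2 gives the outcome as "Pleasant events and activities of person with memory concerns [Time Frame: 3-months and 6-months". The instrument is described as a "17-item self-report survey that measures the degree of enjoyment persons with dementia have engaging in a range of activities". Frequency is not mentioned. The other three outcomes in section 3 (DQoL, the Cantril ladder and social interactions) are all worded as changes and all list baseline; the neighbouring secondary outcome, for example, reads "Change in the frequency and quality of social interactions of persons with memory concerns [Time Frame: Baseline, 3-months, and 6-months". PES-AD is the exception.

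Section 17.1 says: "The PES-AD asks with what frequency and level of enjoyment the person with memory loss experiences a list of pleasant activities". It gives a separate reliability coefficient for each score, .84 for frequency and .76 for enjoyment. For the analysis it states: "Change scores were calculated to determine differences between outcomes at baseline and 6 months". Changes in satisfaction and quality of life are then compared between arms by t test, two-tailed at .05. PES-AD is one of the two instruments named there as measuring quality of life. No 3-month comparison between arms and no multiplicity rule is described.

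Section 5.3 says that the follow-up surveys repeated the baseline survey apart from the demographic questions. Section 17.2 gives no power analysis.

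**The concern.** An outcome is pinned down by its score, its form (level or change) and its time point. For PES-AD all three differ between the section that defines the outcome and the section that analyses it. A reader with a PES-AD result in hand cannot tell from these documents whether it is the secondary result, one of two, or something else.

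The choice between frequency and enjoyment matters most, because section 17.1 describes both and ranks neither. The researchers were not blinded (section 5.2), and section 17.1 is quoted in the past tense from the results paper. The documents therefore do not show that the choice of score was fixed before the data were seen. If both scores are tested at .05, a single favourable result carries a higher false-positive risk than its nominal level.

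**Working it through.** The plan states no power or error-rate figure for this outcome (17.2 is n/a), so there is none to reproduce. The check is a comparison of the text, followed by two short calculations.

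**1. The sections side by side**

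| Feature | Section 3.2 | Section 17.1 |
|---|---|---|
| Score | Enjoyment | Frequency and enjoyment |
| Form | Not worded as change | Change score |
| Baseline | Not listed | Used |
| Times compared between arms | 3 and 6 months listed | 6 months only |

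No other section reconciles the two columns.

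**2. Can the change score be formed?** Section 5.3 does not name PES-AD. Its baseline list includes quality of life, and 17.1 counts PES-AD as a quality-of-life measure. Section 5.3 also says that the baseline and follow-up surveys matched apart from demographics. Both routes imply a baseline PES-AD score, so the missing baseline is a defect in how 3.2 defines the outcome.

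**3. False-positive chance if both scores are tested.** Inputs: two tests, each at two-sided .05 (17.1), with no adjustment stated.

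- Perfectly correlated scores: 0.05.
- Independent scores: 1 − (1 − 0.05)² = 1 − 0.9025 = 0.0975.

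Non-negative correlation puts the value between 5% and 9.75%. The documents give no correlation. Two ratings of the same activities by the same respondent are likely to be positively related, so 9.75% is an upper limit and not an estimate.

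**4. What baseline adjustment would gain.** Let r be the correlation between baseline and 6-month enjoyment. It is not given, so it is varied here. Assume equal variance at both times and set the follow-up variance to 1. The change score then has variance 2(1 − r), and the baseline-adjusted comparison (ANCOVA) has residual variance 1 − r². Their ratio is (1 − r²) / [2(1 − r)] = (1 + r)/2.

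| r (assumed) | Change score | ANCOVA | Ratio |
|---|---|---|---|
| 0.3 | 1.40 | 0.91 | 0.65 |
| 0.5 | 1.00 | 0.75 | 0.75 |
| 0.7 | 0.60 | 0.51 | 0.85 |
| 0.8 | 0.40 | 0.36 | 0.90 |

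Over this range ANCOVA has 10% to 35% less variance than the change score. For r below 0.5 the change score is noisier than the 6-month level alone.

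**The case against.** The case for leaving this alone is substantial, and much of it stands.

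- **Section 17.1 already fixes the form, time and test.** This is correct. A reader might multiply two scores, two times and two forms and infer eight open analyses. The documents do not support that count: 17.1 leaves only the score open, and 3.2 itself names two times.
- **Testing both scores is an inference.** This is correct. Two reliability coefficients and a t test of quality-of-life changes make it likely, but 17.1 does not say that each score was tested separately.
- **The upper limit of 9.75% is not shown to be an increase over 3.2.** This is correct. One score at two times, as 3.2 lists, would also be two tests.
- **The outcome's name is wider than enjoyment.** This is partly right. The enjoyment wording describes the instrument and is not a scoring rule. But it is the only content 3.2 gives, and frequency appears nowhere in it.
- **The untested 3-month point is not peculiar to PES-AD.** This is correct. Section 17.1 uses baseline to 6 months for every outcome.
- **Naming one score now is itself a post hoc choice.** This is correct, and it governs how the fix must be reported.

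Two further readings are tempting. One is that no baseline exists, so the change score is impossible; section 5.3 points the other way. The other is that calling PES-AD a quality-of-life measure raises it to the rank of DQoL. That wording names a domain, and sections 3.1 and 3.2 still set the ranking.

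**Conclusion.** The inconsistency is real and is in the current text: sections 3.2 and 17.1 describe different PES-AD outcomes, and the score that counts as the secondary result is not named. The stakes are small. This is one secondary outcome in a pilot of 48 randomised participants with no power analysis. The error rate of 5% to 9.75% holds only if both scores were tested without adjustment and are not negatively correlated.

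A reader might go further and infer that the score was chosen to suit the data. The documents do not show that. They show only that the choice was not specified, and they contain no PES-AD results from which selection could be judged.

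**What to change.** Reconcile 3.2 and 17.1 in a dated note, labelled post hoc because section 26.1 says the study is complete. The present wording of 3.2 should stay visible and not be overwritten. The note should:

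1. List baseline in the PES-AD time frame alongside 3 and 6 months.
2. Name the enjoyment score at 6 months as the secondary result, compared between arms by ANCOVA with baseline PES-AD enjoyment as covariate, in place of the change-score t test. Enjoyment is the only content 3.2 describes, and 6 months is the only time 17.1 tests, so the choice rests on the documents and not on results.
3. Label the frequency score and the 3-month results exploratory.
4. Report both scores at both times, so that no result is selectively dropped, and say how this differs from 3.2 and from the change-score analysis in 17.1.

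The cost is a small reanalysis plus the disclosure. ANCOVA would be run in each of the five imputed data sets and pooled. No new data are needed, provided that baseline PES-AD was collected as section 5.3 implies; that should be confirmed first.

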4.0 Study Intervention(s)/Interaction(s)

- 4.1 Description:

The social support aid technology consists of a smartphone with a facial recognition software application and a smartwatch. Up to 1,000 individuals can be enrolled in

SOCIAL PROTOCOL (HRP-580)

PROTOCOL TITLE: Social Support Aid for People with Dementia

VERSION DATE: 5/8/2017

the facial recognition application. Enrollment includes typing individuals names and relationships of the person with memory concern into the application and taking pictures of PWMC's faces at multiple angles. Once enrolled and in view of the smartphone's camera, the SSA's application recognizes the individual's face and alerts the smartwatch. The watch then vibrates and displays the individuals' name and relationship to the PWMC.

5.0 Procedures Involved

5.1 Study Design:

A parallel randomized controlled pilot trial design.

5.2 Study Procedures:

“Following completion of the baseline survey, participants were randomly assigned to either receive the technology or to continue with usual care. Participants were randomized at a ratio of 1:1 using a random number generator. Neither the participants nor researchers were blinded to randomization group. Research assistants met with participants in the intervention group in-person to provide the mobile phone and smartwatch and demonstrate how to use the SSA technology. Participants were given the technology to use at their discretion, and there was no requirement for how many times they had to use the SSA. Throughout the study, research assistants and the SSA developer provided technical support and answered questions regarding the technology. Participants in the control group were given the technology free of charge after completing the study.” (see <https://www.ncbi.nlm.nih.gov/pmc/articles/PMC6715400/>)

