5.3 Follow-Up

“Data were collected at three time points: baseline, 3 months, and 6 months. Caregivers completed all surveys on behalf of the person with memory loss. Participants were asked for their opinion of their relative with memory loss (eg “How often does your relative feel confident?”). At baseline, surveys for participants caring for a person with memory loss measured ADLs, memory impairment, memory and problem behaviors, social interaction, and quality of life as well as demographic questions asking about themselves and the person with memory loss. Participants with memory loss who did not have a caregiver completed surveys on their own behalf. They received a slightly different version of the survey with questions being asked in reference to themselves (eg, “How often do you feel confident?”). Their baseline survey measured ADLs, memory impairment, social interaction, and quality of life as well as demographic questions about themselves. Surveys administered at 3 and 6 months were identical to the baseline surveys except that they did not include demographic questions. At 3 and 6 months, participants in the intervention group completed an additional feasibility and utility checklist. Participants were given the option to complete an online or paper version of the surveys.” (see <https://www.ncbi.nlm.nih.gov/pmc/articles/PMC6715400/>)

SOCIAL PROTOCOL (HRP-580)**PROTOCOL TITLE:** Social Support Aid for People with Dementia**VERSION DATE:** 5/8/2017**5.4 Individually Identifiable Health Information**

Survey data per above were relied upon.

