13.0 Withdrawal of Participants

Per <https://www.ncbi.nlm.nih.gov/pmc/articles/PMC6715400/>: "A total of 58 potential participants were assessed for eligibility; of these, all but one met the inclusion criteria. Six of the 58 potential participants were unwilling to provide informed consent and were not included in the study. None of the participants expressed unwillingness to be randomized. Of the 48 participants that were randomized, 44 finished the study (92% retention rate). Two participants with memory loss refused participation after undergoing randomization to the intervention group. Two participants who were caregivers were lost to follow-up, both in the intervention group."

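### The t tests on 6-month change take no account of whether a caregiver or the participant answered; a model with baseline score and respondent type would be more precise at almost no cost

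*Combined protocol and SAP*

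**What the plan says.** - **Allocation (5.2).** "Participants were randomized at a ratio of 1:1 using a random number generator". Randomisation follows the baseline survey. No blocks, strata or minimisation factors are described.
- **Who answers (5.3).** For people with a caregiver: "Caregivers completed all surveys on behalf of the person with memory loss". For the rest: "Participants with memory loss who did not have a caregiver completed surveys on their own behalf", and "They received a slightly different version of the survey with questions being asked in reference to themselves". No count of either type is given.
- **Over time (5.3).** "Surveys administered at 3 and 6 months were identical to the baseline surveys except that they did not include demographic questions".
- **Analysis (17.1).** "Change scores were calculated to determine differences between outcomes at baseline and 6 months". To judge whether changes in the intervention group "were significantly different than changes in the control group, t tests were used". Tests are two-tailed at 0.05, by intention to treat with five-fold multiple imputation. The between-arm baseline comparison covers demographics; no adjustment follows from it and respondent type is not mentioned.
- **Numbers (13.0, 17.2).** "Of the 48 participants that were randomized, 44 finished the study (92% retention rate"). The power analysis is marked as not applicable.

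**The concern.** Respondent type is known before allocation, since a person either has a participating caregiver or does not when the baseline survey is completed. It decides which survey version is used and whose judgement supplies the outcome. Yet it appears in neither the described allocation nor the analysis.

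With 48 people the self/proxy mix can differ between arms by chance. If self-ratings and proxy ratings change by different amounts over six months, part of the observed arm difference in that particular allocation reflects who answered. Any such difference also stays in the error term of an unadjusted test. At stake are precision and the reading of one small trial's estimate.

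**Working it through.** **Inputs.** From the documents: 48 randomised, 1:1 (13.0, 5.2); change from baseline to 6 months, t test, no covariate (17.1); same survey version at each visit (5.3). Assumed, because the documents give no figure: exactly 24 per arm; 8 to 24 self-respondents; SD of change within respondent type = 1; a self/proxy difference in mean change of up to 1 SD. The plan states no power or imbalance figure to reproduce. Its 92% retention checks: 44/48 = 91.7%.

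**1. What cancels.** Let L be a constant self/proxy difference in level and D the self/proxy difference in mean 6-month change. Follow-up differs between types by L + D and baseline by L, so change differs by (L + D) − L = D. With imbalance I (difference between arms in the share of self-respondents), the conditional shift in the arm difference is I × D. L drops out. A simulation with L = 1 SD and D = 0 agrees: the correlation between the estimate and the imbalance was about 0.

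**2. How large an imbalance.** With S self-respondents, the number a in one arm of 24 is hypergeometric (48, S, 24), and I = (2a − S)/24.

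| S (assumed) | P(imbalance of 20 points or more) |
|---|---|
| 8 | 4.8% |
| 12 | 9.3% |
| 16 | 12.5% |
| 24 | 14.8% |

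For these values of S the smallest attainable imbalance above 20 points is 6/24 = 25 points, so the same probabilities apply to 25 points or more.

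**3. Size of the shift.** Standard error of the arm difference: √(1/24 + 1/24) = 0.289 SD.
- 25 points with D = 0.5 SD: 0.25 × 0.5 = 0.125 SD, and 0.125/0.289 = 0.43 SE.
- Typical case: the SD of I is 0.109 (S = 8) to 0.146 (S = 24). Times 0.5 this is 0.05 to 0.07 SD.

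**4. Precision lost by omitting respondent type.** The SE inflation is √(1 + p(1 − p)D²), with p = S/48. At D = 0.5 it is √(1 + 0.139 × 0.25) = 1.017 for S = 8 and √(1 + 0.25 × 0.25) = 1.031 for S = 24.

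**5. Error rate and power.** These come from simulation with 12,000 runs per scenario, coin-flip allocation and no dropout. The adjusted analysis here is the change score with respondent type added.
- Overall type I error of the t test: 4.6% to 5.4%.
- Given an imbalance of 20 points or more: about 5% if D = 0, 5% to 7% if D = 0.5, 9% to 12% if D = 1.
- Power for an assumed 0.8 SD effect with S = 12: unadjusted 76%, 75% and 69% for D = 0, 0.5 and 1; adjusted 75% to 76% throughout.

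**6. Gain from baseline adjustment.** With equal variances and baseline to 6-month correlation r, the variance ratio of the baseline-adjusted model to the change score is (1 − r²)/(2(1 − r)) = (1 + r)/2.
- r = 0.7: √0.85 = 0.922, so the SE is 8% smaller.
- r = 0.3: √0.65 = 0.806, so the SE is 19% smaller. Put the other way, the change-score SE is 1/0.806 = 1.24 times as large.

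**7. Why respondent type must be in that model.** With a fitted baseline slope b, the conditional shift without respondent type is I × [(L + D) − bL] = I × [D + (1 − b)L]. Unless b = 1, part of L returns. For example, I = 0.25, b = 0.7, L = 1 SD and D = 0 (all assumed) give 0.25 × 0.3 = 0.075 SD.

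**The case against.** The strongest defence is that the planned analysis is valid. It tests within-person change on an unchanged survey version, which already removes stable self/proxy differences. Chance imbalance is random error that the t test's standard error covers. The documents give no evidence that change differs by respondent type, and if it does not, adjusting for type gains nothing. The study is a pilot with no power claim. All of this stands, and it limits the point to precision and interpretation.

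A reader might infer more, in four ways that the documents do not support.
- **That mixing two survey versions biases the treatment estimate.** A level difference cancels, and there is no bias averaged over allocations.
- **That allocation was simple and unstratified.** Section 5.2 names a tool and is silent on blocks and strata; silence does not establish their absence.
- **That uneven arm sizes add to the problem.** Under coin-flip allocation there is a 31% chance that the smaller arm has 20 or fewer of 48. But a 20/28 split raises the SE only from 0.289 to √(1/20 + 1/28) = 0.293 SD, and says nothing about respondent type.
- **That the answer is stratified blocks.** The protocol describes a completed study (26.1), so allocation can no longer be changed.

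What survives the defence is that one trial has one allocation. If it was unbalanced and change differs by type, the unadjusted estimate is shifted, and nothing in 17.1 would show it.

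**Conclusion.** The point holds as a modest, inexpensive improvement. The plan describes neither stratification nor adjustment for a factor that is known before randomisation and determines the source of the outcome. The t tests remain valid, with overall type I error near 5%.

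Under an assumed 0.5 SD difference in change, the typical shift is 0.05 to 0.07 SD against an SE of about 0.29 SD. An imbalance of 25 points shifts the estimate by 0.125 SD, about 0.4 SE; one at least that large has probability 5% to 15%. Omitting respondent type then inflates the SE by only 2% to 3%. Most of the gain from the proposed model comes from the baseline score: an SE 8% to 19% smaller for correlations of 0.7 down to 0.3.

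The counts of self-respondents, the 24/24 split, the difference in change and the correlations are all assumptions. The actual counts by arm would settle how much imbalance occurred.

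**What to change.** In 17.1, replace the t test on change with a linear model on the 6-month score containing arm, baseline score and respondent type (self or caregiver proxy). Fit it in each of the five imputed data sets and pool the estimates. Report the number of self and proxy respondents by arm, and state in 5.2 whether blocks or strata were used.

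The cost is SAP wording and one or two degrees of freedom. The baseline score is already collected, and respondent type is known from the survey version each person received.
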